11.4. Appendix 4: Derived and Transformed Data

11.4.1. General

Multiple Measurements at One Time Point

 Mean of the measurements will be calculated and used in any derivation of summary statistics but if listed, all data will be presented. If there are two values within a time window the value closest to the target day for that window will be used. If values are the same distance from the target then the mean will be taken. Subjects having both High and Low values for Normal Ranges at any post-baseline visits for safety parameters will be counted in both the High and Low categories of “Any visit post-baseline” row of related summary tables. This will also be applicable to relevant Potential Clinical Importance summary tables.
Study Day

 Calculated as the number of days from randomisation date : 
 Ref Date = Missing → Study Day = Missing Randomisation Date = Missing → Study Day = Missing Ref Date < Randomisation Date → Study Day = Ref Date – Randomisation Date Ref Date ≥ Randomisation Date → Study Day = Ref Date – (Randomisation Date) + 1

11.4.2. Study Population

Demographics
Age

 GSK standard IDSL algorithms will be used for calculating age where birth date will be imputed as follows: 
 Any subject with a missing day will have this imputed as day ‘15’. Any subject with a missing date and month will have this imputed as ‘30th June’. Birth date will be presented in listings as ‘YYYY’.
Body Mass Index (BMI)

 Calculated as Weight (kg) / [Height (m)²]

Extent of Exposure

 Number of days of exposure to study drug will be calculated based on the formula: Duration of Exposure in Days = Treatment Stop Date – (Treatment Start Date) + 1

 Subjects who were randomized but did not report a treatment start date will be categorised as having zero days of exposure.

 The cumulative dose will be based on the formula: Cumulative Dose = Sum of (Number of Days x Total Daily Dose)

 If there are any treatment breaks during the study, exposure data will be adjusted accordingly.


Tolerability will be assessed with the skin irritation scoring system for Part A and B of study, where the score consists of a numeric score according to the dermal response scoring i), and a letter according to the other effects scoring ii), as follows
 
0 = no evidence of irritation 1 = minimal erythema, barely perceptible (pink) 2 = moderate erythema (definite redness), readily visible; minimal edema or minimal papular response 3 = strong erythema (intense redness), or erythema and papules 4 = definite edema 5 = erythema, edema, and papules 6 = vesicular eruption 7 = strong reaction spreading beyond test site
 
ii) Other effects:
 
Z = no other effect A = slight glazed appearance B = marked glazing C = glazing with peeling and cracking F = glazing with fissures G = film of dried serous exudate covering all or part of the patch site H = small petechial erosions and/or scabs
 
For each skin assessment, letter grade will be converted to numeric values as below: A=0, Z=0, B=1, C=2, F=3, G=3, H=3. A combined score for each subject will be calculated by adding all numeric and letter scores. A maximum score of 3 is allowed. Mean irritation score for each subject will be computed through the study period. Mean score will be analyzed.

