## 2. OBJECTIVE(S) AND ENDPOINT(S)

### 2.1. Primary objectives and endpoints for all study parts (A, B & C)

Objectives	Endpoints

Safety and Tolerability
 
To investigate the safety and tolerability of topically applied GSK2646264 cream and its placebo in healthy subjects, subjects with cold urticaria (CU1) and subjects with chronic spontaneous urticaria (CsU).
	
Safety and Tolerability
 
 
Number, severity and frequency of AEs and serious AEs (local and systemic)
 
heart rate
 
blood pressure
 
12- lead ECG
 
clinical laboratory safety tests
 
assessment of the local tolerability of the study medication
 

1. All Healthy subjects and the Cold urticaria subjects should be screened for reactivity to one of the allergens used in skin prick test. (grass pollen, Dermatophagoides pteronyssinus, birch pollen and cat dander)

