7. PRIMARY STATISTICAL ANALYSES

7.1. Safety Analyses

7.1.1. Overview of Planned Analyses

The safety analyses will be based on the ‘Safety’ population, unless otherwise specified.

Table 3 provides an overview of the planned analyses, with further details of data displays being presented in [Appendix 10: List of Data Displays](#).

Table 3 Overview of Planned Safety Analyses for Part A, B and C of study

Endpoint / Parameter/ Display Type	Absolute				Change from Baseline			
	Summary		Individual		Summary		Individual	
	T	F	F	L	T	F	F	L
Drug Exposure								
Exposure to Study Drug	Y				Y			
Adverse Events								
Summary of All Adverse Events	Y				Y			
Drug-Related Adverse Events	Y							

Endpoint / Parameter/ Display Type	Absolute				Change from Baseline			
	Summary		Individual		Summary		Individual	
	T	F	F	L	T	F	F	L
Summary of All Localised Adverse Events	Y							
Serious Adverse Events	Y			Y				
AEs Leading to Discontinuation	Y			Y				
AE by Maximum Intensity	Y							
Clinical Laboratory Assessments								
Clinical Chemistry	Y			Y	Y			Y
Haematology	Y			Y	Y			Y
Urinalysis	Y			Y ¹	Y			
Electrocardiogram (ECG)								
ECG Findings	Y			Y	Y			Y
ECG Values	Y			Y	Y			Y
Vital Signs								
Vital Signs	Y			Y	Y			Y
Tolerability assessment								
Tolerability scores	Y			Y	Y			Y

NOTES :

- T = Table, F = Figure, L = Listing, Y = Yes display generated.
- Stats Analysis = Represents TFL related to any formal statistical analyses (i.e. modelling) conducted.
- Summary = Represents TFL related to any summaries (i.e. descriptive statistics) of the observed raw data.
- Individual = Represents FL related to any displays of individual subject observed raw data.
- Tolerability analyses will be produced for Part A and B only.

1 Urinalysis will only list abnormal assessments

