3.15.	Safety	EG2	Summary (Absolute and Change from Baseline) of ECG Values	Please only include Total column (not treatment columns).Order parameters alphabetically	IA[1],SAC [1]
Vital Signs					
3.16.	Safety	VS1	Summary (Absolute and Change from Baseline) of Vital Signs	Please only include Total column (not treatment columns).Order parameters alphabetically	IA[1],SAC [1]
Tolerability assessment					
3.17.	Safety	Non- Standard SAFE_T1	Summary (Absolute and Change from Baseline) of Mean irritation score assessment		IA[1],SAC [1]

Safety : Tables				
No.	Population	IDSL / TST ID / Example Shell	Title	Programming Notes
Deliverable [Priority]				
3.18.	Safety	Non- Standard SAFE_T2	Assessment of Maximum Dermal Reactions and Response	IA[1],SAC [1]

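### The SAP summarises no local tolerability scores for Part C, although they belong to the primary endpoint there, and its mean irritation score is capped at 3 on a 0 to 10 sum

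*SAP*

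**What the plan says.** Protocol section 2.1 lists "assessment of the local tolerability of the study medication" among the primary endpoints for all three parts, and SAP section 2.2 repeats it. The Part C schedule in protocol section 6.1.4 places a tolerability assessment on each dosing day (Days 1, 4 and 7). Protocol section 9.3.2.1 commits to summarising skin reaction assessments by BSA and, where possible, by strength. It exempts no part.

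Table 3 in SAP section 7.1.1 is titled for Parts A, B and C and has a tolerability row, but a note beneath it says "Tolerability analyses will be produced for Part A and B only". SAP section 11.4.3 likewise introduces the scoring for Parts A and B.

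The score is built in SAP section 11.4.3. The dermal grade runs from 0 up to "7 = strong reaction spreading beyond test site". The letter grade is converted by "A=0, Z=0, B=1, C=2, F=3, G=3, H=3". The grade and the converted letter are then summed, subject to a ceiling: "A maximum score of 3 is allowed". The capped sums are finally averaged over time, since the SAP goes on to say "Mean irritation score for each subject will be computed through the study period".

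The resulting mean is the quantity to be analysed. It appears in Table 3.17, "Summary (Absolute and Change from Baseline) of Mean irritation score assessment". Table 3.18 counts subjects by maximum dermal grade, and Listing 28 lists scores by subject, treatment and visit.

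**The concern.** A component of the primary endpoint is collected in a cohort and then excluded from summary, with no reason given. Part C is a parallel, placebo-controlled cohort whose disease itself produces skin lesions. A display by arm is what would let a reader separate a reaction to the cream from background urticaria.

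The secondary concern is that the score named for analysis in Parts A and B stops rising at 3. Reactions that the protocol grades very differently then receive the same value, and averaging over time dilutes them further.

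**Working it through.** **Part C: the documents side by side**

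| Question | Source | Answer |
|---|---|---|
| Is it a primary endpoint in Part C? | Protocol 2.1, SAP 2.2 | Yes |
| Is it collected in Part C? | Protocol 6.1.4 | Yes, on 3 dosing days |
| Was it collected in the schedule the SAP itself reproduces? | SAP 11.2.1.4, note 8 | Yes, as a note to the AE row |
| Does the protocol's analysis section exempt Part C? | Protocol 9.3.2.1 | No |
| Is it summarised in Part C? | SAP 7.1.1, 11.4.3 | No |

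Size: 16 subjects × 3 days = 48 planned scores. At 3:1 allocation that is 12 × 3 = 36 on active and 4 × 3 = 12 on placebo, assuming full recruitment and attendance.

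**The cap**

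Inputs: 8 dermal grades (0 to 7) and 7 letters with values Z=0, A=0, B=1, C=2, F=3, G=3, H=3. That gives 8 × 7 = 56 pairs, and the largest sum is 7 + 3 = 10. The analysed score is min(sum, 3), applying the cap to the combined score at each assessment.

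Pairs with a sum of at least 3:

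- dermal 3 to 7, any letter: 5 × 7 = 35
- dermal 2 with B, C, F, G or H: 5
- dermal 1 with C, F, G or H: 4
- dermal 0 with F, G or H: 3

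The total is 35 + 5 + 4 + 3 = 47 of 56. Seven of these sum to exactly 3 and 40 are cut down to it. The capped score has 4 levels and the uncapped sum has 11.

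The tolerability grades in the dose-limiting definition (protocol section 5.5.1) are dermal 3 or higher together with C, F, G or H. That is 5 × 4 = 20 pairs, with sums from 5 to 10, and all become 3. The other 47 − 20 = 27 pairs at the cap do not reach those grades; examples are 3/Z, 1/C and 0/F.

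**Averaging, as an illustration only**

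Part A group 1 has 3 dosing days with a pre-dose and a 6-hour score, so 6 assessments. Assume all 6 count, one is 6/H (6 + 3 = 9) and the other five are 0.

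- Capped mean: 3/6 = 0.5
- Uncapped mean: 9/6 = 1.5
- Comparison subject with grade 1/Z at three assessments: (1 + 1 + 1)/6 = 0.5

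The result moves with the assumptions. Counting only the three post-dose scores gives 3/3 = 1.0 capped and 9/3 = 3.0 uncapped. If the reaction follows the Day 1 dose and scoring stops there, the two available scores give 3/2 = 1.5 and 9/2 = 4.5.

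**Text against shell**

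SAP section 11.4.3 describes one mean per subject over the study, but the Table 3.17 shell has a Visit column. Neither tolerability shell has a BSA dimension. In each Part A dose group the visit fixes the planned BSA, so a by-visit table would carry it and a study-period mean would not. In Part B, BSA also differs between the first 4 subjects (10%) and the remaining 8 (3.5%), so even a by-visit table would mix the two.

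**The case against.** The strongest reply is that the score is not the only route by which tolerability is reported.

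- A reader might infer that severe local reactions are flattened throughout the reporting. The documents do not support that. In Parts A and B, Table 3.18 keeps maximum dermal grades 1 to 7 and adds a severe-reaction row with mean time to reaction, and Listing 28 gives scores by subject and visit. Only Table 3.17 uses the capped mean. What stands is that Table 3.18 does not show letters separately, and that its severe row (dermal 3 or higher, or F, G or H) does not match the grades in protocol section 5.5.1, so the two should be reconciled.
- A reader might also infer that a Part C primary endpoint goes wholly unanalysed. That is too strong. Local tolerability is one of six listed safety components, and localised AEs (Table 3.4) are summarised for all parts. AE reporting is not a substitute, however. Protocol section 7.1.3 ties automatic AE reporting of skin scores to dermal 2 or higher and a letter of C, F, G or H. Read literally, a 6/Z score does not trigger it.
- The SAP is based on protocol amendment 2 and plans 12 subjects in Part C, so the figure of 16 comes from a later amendment. That accounts for the count but not for the exclusion, because the SAP's own Part C schedule already includes tolerability.
- Protocol section 9.3.2.1 leaves some discretion over which safety assessments are summarised. It does not use that discretion to exempt Part C.
- The cap may follow an established scoring convention. The protocol's reference list includes a regulatory guidance on skin irritation testing, but whether the cap comes from it cannot be checked here. Adding two ordinal scales is itself debatable, and an uncapped mean still dilutes. This objection largely stands: removing the cap outright is partly preference.
- The analysis is descriptive, so no test or error rate is affected. That is correct.

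**Conclusion.** The Part C omission holds and carries the point: a primary-endpoint component is collected on three days in up to 16 subjects, and the SAP excludes it from the score summaries without a reason. It should be corrected before the Part C outputs are produced.

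The cap is a real but smaller defect, confined to the mean irritation score in Table 3.17. That score gives 47 of 56 pairs the same top value and cannot separate the 20 pairs at the dose-limiting tolerability grades from 27 others. The count treats each possible pair once and says nothing about how often each occurs. It also reads the cap as applying to the combined score; applied to the letter alone it would have no effect, since letters already stop at 3. The 0.5 against 1.5 contrast is an illustration that assumes six scored assessments with the other five at 0, and should not be quoted without that label.

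Whether the mean is per visit or per study is unresolved in the SAP, so Table 3.17 cannot be programmed unambiguously.

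**What to change.** 1. Delete the restriction to Parts A and B in SAP sections 7.1.1 and 11.4.3. Produce Tables 3.17 and 3.18 and Listing 28 for Part C by arm.
2. State how change from baseline is handled in Part C. In protocol section 6.1.4 the row label says pre-dose while its footnote gives 1 to 2 hours post-dose; these must be reconciled. If no pre-dose score exists, show absolute scores only.
3. Beside the capped mean, report the uncapped or maximum combined post-dose score by visit, strength and BSA, in line with protocol section 9.3.2.1. Give the reason for the cap.
4. Say whether the mean is per visit or over the study and which assessments enter it, and align section 11.4.3 with the Table 3.17 shell.

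The cost is SAP wording and programming, with no new data. The downsides are a second summary of the same scores and a Part C placebo column of about four subjects, which supports description only.

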11.5. Appendix 5: Premature Withdrawals & Handling of Missing Data

11.5.1. Premature Withdrawals

Element	Reporting Detail
General	
 Subject study completion (i.e. as specified in the protocol) was defined as subjects who completed all visits of the study including the follow-up visit. Withdrawn subjects were not replaced in the study. All available data from subjects who were withdrawn from the study will be listed and all available planned data will be included in summary tables and figures, unless otherwise specified.

11.5.2. Handling of Missing Data

Element	Reporting Detail
General	
 Missing data occurs when any requested data is not provided, leading to blank fields on the collection instrument : 
 These data will be indicated by the use of a "blank" in subject listing displays. Unless all data for a specific visit are missing in which case the data is excluded from the table. Answers such as "Not applicable" and "Not evaluable" are not considered to be missing data and should be displayed as such.
Outliers	
 Any subjects excluded from the summaries and/or statistical analyses will be documented along with the reason for exclusion in the clinical study report.
UAS7 score	
In presence of one or more missing daily UAS7 scores, the following algorithm will be applied:
 
 If a patient has at least 4 non-missing daily UAS7 scores within the 7 days, the UAS7 score will be calculated as the sum of the available eDiary UAS7 scores in that week, divided by the number of days that have a non-missing diary UAS7 score, multiplied by 7. If there are less than 4 non-missing daily UAS7 scores, then the UAS7 score will be missing.
AAS	Missing values will not be imputed
DLQI	
 If one question is left unanswered this is scored 0 and the scores are summed and expressed as usual out of a maximum of 30. If two or more questions are left unanswered the questionnaire is not scored. If question 7 is answered 'yes' this is scored 3. If question 7 is answered 'no' or 'not relevant' but then either 'a lot' or 'a little' is ticked this is then scored 2 or 1. If it is answered 'no', but the second half is left incomplete, the score will remain 0. If two or more response options are ticked, the response option with the highest score should be recorded. If there is a response between two tick boxes, the lower of the two score options

Element	Reporting Detail
	
should be recorded.
 
6. When using sub-scales, if the answer to one question in a sub-scale is missing, that sub-scale should not be scored.

11.5.2.1. Handling of Missing Dates

Element	Reporting Detail
General	Partial dates will be displayed as captured in subject listing displays.
Adverse Events	
 The eCRF allows for the possibility of partial dates (i.e., only month and year) to be recorded for AE start and end dates; that is, the day of the month may be missing. In such a case, the following conventions will be applied for calculating the time to onset and the duration of the event: 
 Missing Start Day: First of the month will be used unless this is before the start date of study treatment; in this case the study treatment start date will be used and hence the event is considered On-treatment. Missing Stop Day: Last day of the month will be used, unless this is after the stop date of study treatment; in this case the study treatment stop date will be used. Completely missing start or end dates will remain missing, with no imputation applied. Consequently, time to onset and duration of such events will be missing. Start or end dates which are completely missing (i.e. no year specified) will remain missing, with no imputation applied.

11.5.2.2. Handling of Partial Dates

Element	Reporting Detail
Concomitant Medications	
 Partial dates for any concomitant medications recorded in the CRF will be imputed using the following convention: 
 If the partial date is a start date, a '01' will be used for the day and 'Jan' will be used for the month If the partial date is a stop date, a '28/29/30/31' will be used for the day (dependent on the month and year) and 'Dec' will be used for the month. The recorded partial date will be displayed in listings.
Adverse Events	
 Any partial dates for adverse events will be raised to data management. If the full date cannot be ascertained, the following assumptions will be made: 
 If the partial date is a start date, a '01' will be used for the day and 'Jan' will be used for the month. However, if these results in a date prior to Week 1 Day 1 and the event could possibly have occurred during treatment from the partial information, then the Week 1 Day 1 date will be assumed to be the start date. The AE will then be considered to start on-treatment (worst case). If the partial date is a stop date, a '28/29/30/31' will be used for the day (dependent on the month and year) and 'Dec' will be used for the month. The recorded partial date will be displayed in listings.

11.6. Appendix 6: Values of Potential Clinical Importance

11.6.1. Laboratory Values

Haematology				
Laboratory Parameter	Units	Category	Clinical Concern Range	
			Low Flag (< x)	High Flag (>x)
Hematocrit	Ratio of 1	Male		0.54
		Female		0.54
		Δ from BL	↓ 0.075	
Hemoglobin	g/L	Male		180
		Female		180
		Δ from BL	↓ 25	
Lymphocytes	x10 ⁹ / L		0.8	
Neutrophil Count	x10 ⁹ / L		1.5	
Platelet Count	x10 ⁹ / L		100	550
White Blood Cell Count (WBC)	x10 ⁹ / L		3	20
Red Blood Cell Count (RBC)	x10 ⁶ cells/µL		4.2	5.9
Mean Corpuscular Volume (MCV)	fL		80	100
Mean Corpuscular Hemoglobin (MCH)	pg		28	32
Mean Corpuscular Hemoglobin Concentration (MCHC)	g/L		32	36
Monocytes	x10 ⁹ / L			0.208
Eosinophils	x10 ⁹ / L			0.44
Basophils	x10 ⁹ / L			0.01

Clinical Chemistry				
Laboratory Parameter	Units	Category	Clinical Concern Range	
			Low Flag (< x)	High Flag (>x)
Albumin	g/L		30	
Calcium	mmol/L		2	2.75
Creatinine	mmol/L			1.3*ULN
	µmol/L			159
	µmol/L	Δ from BL		44
Glucose	mmol/L		3	11.1
Potassium	mmol/L		3	5.5
Sodium	mmol/L		130	150

Liver Function				
Test Analyte	Units	Category	Clinical Concern Range	

Liver Function			
Test Analyte	Units	Category	Clinical Concern Range
ALT/SGPT	U/L	High	$\geq 2x$ ULN
AST/SGOT	U/L	High	$\geq 2x$ ULN
AlkPhos	U/L	High	$\geq 1.5x$ ULN
T Bilirubin	$\mu\text{mol}/\text{L}$	High	$\geq 1.5x$ ULN
T. Bilirubin + ALT	$\mu\text{mol}/\text{L}$ U/L	High	$1.5x$ ULN T. Bilirubin + $\geq 2x$ ULN ALT
Urea Nitrogen (BUN)	mmol/L	Low	<2.9
Urea Nitrogen (BUN)	mmol/L	High	>7.1
Chloride	mmol/L	Low	<98
	mmol/L	High	>106
Gamma-glutamyl Transpeptidase (GGT)	U/L	Low	<8
	U/L	High	>78
Direct Bilirubin	$\mu\text{mol}/\text{L}$	High	>5.1
Total Protein	g/L	Low	<60
	g/L	High	>78

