### 6.3.4. Clinical Laboratory Assessments

Haematology, clinical chemistry, urinalysis and additional parameters to be tested are listed below. Details for the preparation and shipment of samples will be provided by the local laboratory. Reference ranges for all safety parameters will be provided to the site by the laboratory.

If additional non-protocol specified laboratory assessments are performed at the site's local laboratory and result in a change in subject management or are considered clinical significant by the Investigator (for example SAE or AE or dose modification) the results must be captured and sent to GSK along with other study data as defined in Section 7 Haematology, clinical chemistry, urinalysis and additional parameters to be tested are listed below:

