2.4. Statistical Hypotheses

The primary focus of the statistical analysis is to describe safety and characterize the preliminary pharmacokinetics of GSK2646264 through estimates of parameters and their variability. Thus, an estimation approach will be taken and 95% confidence intervals will be constructed to provide a plausible range of values, where appropriate, with no formal hypothesis testing. Sample size estimations and results of succeeding sensitivity analyses are given in 9.2 of the protocol.

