11.10.6. Safety Tables

Safety : Tables					
No.	Population	IDSL / TST ID / Example Shell	Title	Programming Notes	Deliverable [Priority]
Drug Exposure					
3.1.	Safety	EX1	Summary of Exposure to Study Drug	Please only include Total column (not treatment columns)	IA[1],SAC [1]
Adverse Events					
3.2.	Safety	CP_AE1p	Summary of All Adverse Events	Please only include Total column (not treatment columns)	IA[1],SAC [1]
3.3.	Safety	CP_AE1p	Summary of Drug-Related Adverse Events	Please only include Total column (not treatment columns)	IA[1],SAC [1]
3.4.	Safety	CP_AE1p	Summary of All Localised Adverse Events		IA[1],SAC [1]
3.5.	Safety	CP_AE1p	Summary of Serious Adverse Events	Please only include Total column (not treatment columns)	IA[1],SAC [1]
3.6.	Safety	CP_AE1p	Summary of AEs Leading to Permanent Discontinuation of Study Drug or Withdrawal from Study	Please only include Total column (not treatment columns)	IA[1],SAC [1]
3.7.	Safety	AE5	Summary of Adverse Events by Maximum Intensity/Grade	Please only include Total column (not treatment columns)	IA[1],SAC [1]
3.8.	Safety	AE2	Relationship between System Organ Class and Verbatim Text		IA[1],SAC [1]
Clinical Laboratory Assessments					
3.9.	Safety	LB1	Summary (Absolute and Change from Baseline) of Clinical Chemistry Laboratory Values	Please only include Total column (not treatment columns). Order parameters alphabetically	IA[1],SAC [1]

Safety : Tables					
No.	Population	IDSL / TST ID / Example Shell	Title	Programming Notes	Deliverable [Priority]
3.10.	Safety	LB2	Summary of Clinical Chemistry Data Outside the Reference Range	Order parameters alphabetically	IA[1],SAC [1]
3.11.	Safety	LB1	Summary (Absolute and Change from Baseline) of Haematology Laboratory Values	Please only include Total column (not treatment columns).Order parameters alphabetically	IA[1],SAC [1]
3.12.	Safety	LB2	Summary of Haematology Data Outside the Reference Range	Order parameters alphabetically	IA[1],SAC [1]
3.13.	Safety	UR3	Summary of Urinalysis Dipstick Results	Please only include Total column (not treatment columns).Order parameters alphabetically	IA[1],SAC [1]
Electrocardiogram (ECG)					
3.14.	Safety	EG1	Summary (Absolute and Change from Baseline) of ECG Findings	Please only include Total column (not treatment columns).Order parameters alphabetically	IA[1],SAC [1]

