11.10.12. ICH Listings

ICH : Listings					
No.	Population	IDSL / TST ID / Example Shell	Title	Programming Notes	Deliverable [Priority]
Randomisation					
1.	Safety	CP_TA1	Listing of Randomised and Actual Treatments		IA [1], SAC [1]
Subject Disposition					
2.	Safety	ES7	Listing of Reasons for Screen Failure		IA [1], SAC [1]
3.	Safety	ES2	Listing of Reasons for Withdrawal		IA [1], SAC [1]
4.	Safety	DV2	Listing of Important Protocol Deviations		IA (SAC)
5.	Safety	ES2	Listing of Exclusions from Per Protocol Population		IA (SAC)
Inclusion and Exclusion Criteria					
6.	Safety	IE3	Listing of Subjects with Inclusion/Exclusion Criteria Deviations		IA [1], SAC [1]
Demographics					
7.	Safety	DM2	Listing of Demographic Characteristics		IA [1], SAC [1]
8.	Safety	DM9	Listing of Race		IA [1], SAC [1]
Medical History					
9.	Safety	MH2	Listing of Medical History		IA [1], SAC [1]
Concomitant Medication					
10.	Safety	CP_CM3	Listing of Concomitant Medication by Generic Term		IA [1], SAC [1]
Study Drug Exposure					
11.	Safety	EX3	Listing of Exposure Data	If applicable adapt to study data	IA [1], SAC [1]

ICH : Listings					
No.	Population	IDSL / TST ID / Example Shell	Title	Programming Notes	Deliverable [Priority]
Adverse Events					
12.	Safety	AE7	Listing of All Adverse Events		IA [1], SAC [1]
13.	Safety	CP_AE8	Listing of Subject Numbers for Individual Adverse Events		IA [1], SAC [1]
14.	Safety	CP_AE8a	Listing of Serious Adverse Events		IA [1], SAC [1]
15.	Safety	CP_AE8	Listing of Adverse Events Leading to Withdrawal from Study		IA [1], SAC [1]
Clinical Laboratory Assessments					
16.	Safety	CP_LB5	Listing of Haematology Abnormalities of Potential Clinical Importance		IA [1], SAC [1]
17.	Safety	CP_LB5	Listing of All Haematology Laboratory Data for Subjects with Abnormalities of Potential Clinical Importance	Including change from Baseline	IA [1], SAC [1]
18.	Safety	CP_LB5	Listing of Clinical Chemistry Abnormalities of Potential Clinical Importance		IA [1], SAC [1]
19.	Safety	CP_LB5	Listing of Clinical Chemistry Laboratory Data for Subjects with Abnormalities of Potential Clinical Importance	Including change from Baseline	IA [1], SAC [1]
20.	Safety	CP_LB5	Listing of All Hematology Laboratory Data for Subjects with Adverse Events of Interest		IA [1], SAC [1]
21.	Safety	UR2b	Listing of Urinalysis Data for Subjects with Abnormalities of Potential Clinical Concern		IA [1], SAC [1]
Electrocardiogram (ECG)					

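### The MCHC flag limits in SAP 11.6.1 (32 and 36 g/L) disagree by a factor of ten with the other red-cell limits in the same table

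*SAP*

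**What the plan says.** SAP section 11.6.1 (Appendix 6) tabulates haematology limits. A value below the low flag or above the high flag is of potential clinical importance. For the row that begins "Mean Corpuscular Hemoglobin Concentration (MCHC" the unit is g/L, the low flag 32 and the high flag 36.

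The same table covers the quantities from which MCHC is calculated:

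- Haemoglobin: g/L, high flag 180 for both sexes, with a fall from baseline of 25 also flagged.
- Haematocrit: expressed as a ratio, high flag 0.54.
- The row beginning "Mean Corpuscular Hemoglobin (MCH": pg, limits 28 and 32.
- The row beginning "Mean Corpuscular Volume (MCV": fL, limits 80 and 100.
- Red cell count: millions per microlitre, limits 4.2 and 5.9.

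By their titles, two displays in SAP 11.10.12 rest on these limits: Listing 16, "Listing of Haematology Abnormalities of Potential Clinical Importance", and Listing 17, "Listing of All Haematology Laboratory Data for Subjects with Abnormalities of Potential Clinical Importance". Both are assigned to the interim and final deliveries. By contrast, Table 3.12 in SAP 11.10.6, "Summary of Haematology Data Outside the Reference Range", uses laboratory ranges. On those, protocol section 6.3.4 says that "Reference ranges for all safety parameters will be provided to the site by the laboratory". Neither document states the unit in which the laboratory reports MCHC.

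**The concern.** MCHC is not free to take any value once haemoglobin and haematocrit, or MCH and MCV, are known. Limits for it must therefore sit on the same scale as theirs, and here they do not. Clinical laboratory tests are among the primary safety endpoints, and these limits were fixed in advance to pick out results for individual review. A limit that almost any result exceeds selects nothing. Listing 17 is the more exposed of the two listings, because one flagged value brings in all of that subject's haematology data.

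**Working it through.** **Printed figure.** Low 32, high 36, unit g/L. It cannot be reproduced from the rest of the table in that unit.

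**Identities.** MCHC is haemoglobin mass per unit volume of packed red cells, so:

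- MCHC (g/L) = Hb (g/L) / Hct (ratio)
- MCHC (g/L) = 1000 × MCH (pg) / MCV (fL)

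These are definitions and need no outside reference range.

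**Check 1, haemoglobin and haematocrit limits.** 180 / 0.54 = 333.3 g/L, which is 33.3 g/dL. Relative to the high flag: 333.3 / 36 = 9.3.

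**Check 2, MCH and MCV limits.**

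- Smallest: 1000 × 28 / 100 = 280 g/L, and 280 / 36 = 7.8
- Middle: 1000 × 30 / 90 = 333.3 g/L
- Largest: 1000 × 32 / 80 = 400 g/L, and 400 / 36 = 11.1

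A subject whose MCH and MCV both lie within the SAP's own limits therefore has an MCHC 7.8 to 11.1 times the high flag. The two ends pair opposite extremes, so they bound the range and are not typical values.

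**Check 3, are the other rows on a common scale?** MCH × red cell count gives haemoglobin from 28 × 4.2 = 117.6 g/L to 32 × 5.9 = 188.8 g/L. MCV × red cell count / 1000 gives haematocrit from 80 × 4.2 / 1000 = 0.336 to 100 × 5.9 / 1000 = 0.59. The printed limits of 180 g/L and 0.54 fall inside these ranges. The other rows agree with each other, and the MCHC row is the odd one out.

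**What would escape the high flag?** At Hct 0.54, haemoglobin would have to be at most 36 × 0.54 = 19.4 g/L. That is less than the 25 g/L fall that the same table treats as notable. At MCV 80 to 100 fL, MCH would have to be at most 36 × 80 / 1000 = 2.9 pg to 36 × 100 / 1000 = 3.6 pg, against a lower limit of 28 pg. Direction is lost as well: 280 g/L is below 320 g/L, yet it would be flagged high.

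**Same limits read as g/dL.** 32 to 36 g/dL is 320 to 360 g/L. The 333.3 g/L from check 1 and from the middle of check 2 lies inside. The discrepancy is a factor of ten.

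**Number of subjects.** Protocol section 9.2 plans 18 in Part A, 12 in Part B and 16 in Part C: 18 + 12 + 16 = 46. (The same section gives a total of about 42, which does not equal its own components; 46 is used here as the ceiling.) An interim delivery on Part A alone would involve up to 18.

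**The case against.** The inconsistency itself is hard to dispute. The neighbouring units read sensibly, nothing suggests a shifted column or a redaction, and no other section corrects the row. The serious objections are to its consequences, and most of them stand.

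- **Mass flagging is conditional.** It needs MCHC values held in g/L. If results arrive in g/dL and are compared unconverted, 32 and 36 work as limits and only the label is wrong. A reader might infer that every subject will be flagged. The documents do not support that without the condition, although a programmer who follows the SAP literally would work in g/L.
- **Other signals are not hidden.** Protocol Table 6 names neutropenia as a risk, so a reader might infer that the listings could no longer reveal it. They could: neutrophils have their own limit (below 1.5 × 10⁹/L), and such a result enters Listing 16 whatever happens to MCHC. The harm is added noise.
- **Other displays are intact.** Table 3.11 gives values and changes from baseline, Table 3.12 uses reference ranges, and Listing 20 is driven by adverse events. Investigators also report clinically significant laboratory abnormalities as adverse events (protocol section 7.1.3).
- **No decision depends on the limit.** The SAP takes an estimation approach with "no formal hypothesis testing", and safety data are summarised descriptively. The stopping and progression rules in protocol sections 5.5 to 5.8 do not use it.
- **The scale is small.** At worst, Listing 17 becomes a full haematology listing of some 46 people, and SAP Table 3 already plans individual haematology listings.

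These points limit the severity. They do not make the row correct, because in its printed unit it gives a wrong flag.

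**Conclusion.** The row is wrong as written: in its stated unit, the limits are a tenth of what the rest of the table implies. That conclusion rests only on the SAP's own figures and the definition of MCHC.

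The effect depends on one fact that the documents do not give. With MCHC held in g/L, essentially every subject with a result would be flagged high, Listing 16 would carry spurious MCHC rows, and Listing 17 would lose its subject-level selectivity. With MCHC held in g/dL and unconverted, the listings would be right and the printed unit wrong. In neither case does an estimate, a confidence interval or a rule for running the trial change. Severity is minor.

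**What to change.** Confirm the unit in which MCHC is held in the analysis dataset, including any conversion from the laboratory's unit. Then correct the row in SAP 11.6.1 to match: 32 and 36 with the unit g/dL, or 320 and 360 with the unit g/L. Record the reporting unit in the SAP so that the listing program and the table agree.

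The cost is one query to data management and a correction to one row. No data collection, trial procedure or other analysis changes. If either listing has already been produced with the limits applied to g/L values, it needs to be rerun.
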